#### **8.2.4 Oral swabs for NAAT-based SARS-CoV-2 testing for screening and surveillance**

Oral swabs for (NAAT-based) SARS-CoV-2 testing will be collected by trial site personnel at the time points provided in the SoA (Section 1.3).

The NAAT-based analysis of oral swabs for SARS-CoV-2 will be performed by a local laboratory. The most commonly used devices eventually come with pre-defined test panels that test for a range of pathogens and not just for SARS-CoV-2. Thus, inevitably and automatically, incidental data for the pathogens other than SARS-CoV-2 will be generated when using such devices. Since this incidental data is not required by this trial, only the results for SARS-CoV-2 will be recorded in the CRF, analyzed, and reported as described in this protocol. If a test result for SARS-CoV-2 or another pathogen must be reported to relevant authorities, this notification will be done by the trial site.

Additionally, any potentially SARS-CoV-2 – infected and/or symptomatic trial subjects will be asked to return *ad hoc* to the site for SARS-CoV-2 diagnostics as soon as possible. Oral swabs for SARS-CoV-2 genomic sequencing will also be collected and analyzed at a later time point at a central laboratory.

Instructions on the sample handling and shipping to the analysis site will be provided in a Laboratory Manual. The methodology used includes NAAT-based analysis and SARS-CoV-2 digital drop polymerase chain reaction (ddPCR).

The below definition of “confirmed COVID-19” cases for the purpose of surveillance during the trial is based on the US FDA guidance for Industry “[Development and Licensure of Vaccines to Prevent COVID-19](#)”.

Confirmed COVID-19: presence of one or more of the below symptoms and SARS-CoV-2 NAAT positive test either at the central laboratory or at a local testing facility (using a certified test):

- Fever or chills
- New or increased cough
- New or increased shortness of breath or difficulty breathing
- Fatigue
- Headache
- New or increased muscle or body aches (pain)
- New loss of taste or smell
- Sore throat
- Congestion or runny nose
- Nausea or vomiting
- Diarrhea

### **8.2.5 Serological testing for SARS-CoV-2 N-binding antibodies**

Blood will be drawn by trial site personnel for serological testing for SARS-CoV-2 N-binding antibodies by serum SARS-CoV-2 nucleocapsid protein enzyme-linked immunosorbent assay (ELISA) testing at the time points provided in the SoA (Section 1.3). SARS-CoV-2 nucleocapsid protein ELISA testing will be performed at a central laboratory (not applicable for Part C screening).

### **8.2.6 SARS-CoV-2 sequencing**

Swabs for SARS-CoV-2 genomic sequencing storage will be collected by trial site personnel at the time points provided in SoA (Section 1.3).

The swabs will be inserted into collection tubes pre-filled with stabilizer solution. The swabs must be stored in the central laboratory at a minimum -70°C/-94°F until the end of the trial.

SARS-CoV-2 genomic sequencing including SARS-CoV-2-ddPCR will be performed, even if no COVID-19 symptoms are shown.

Instructions on the sample handling and shipping to the analysis site will be provided in a Laboratory Manual.

The outcome of SARS-CoV-2 genomic sequencing would be SARS-CoV-2 S antigen sequences and/or whole genome sequences and assigned (where possible) to known viral variants.

## **8.3 Adverse events and SAEs**

The investigator and any qualified designees are responsible for detecting, documenting, and recording events that meet the definition of an AE or SAE or AESI and are responsible for following up all AEs and SAEs.

Solicited events that are derived from the subject e-diaries should not be additionally reported as AEs unless the event meets criteria for an SAE or starts after Day 7 or starts on Days 1 to 7 and continues past Day 7.

In addition, all solicited Grade 4 events need to be medically confirmed.

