### 8.2.3.2 Assessments of intensity for systemic reactions

#### *Symptoms of systemic reactions*

Symptoms of systemic reactions will be assessed by the trial subject as absent, mild, moderate, severe, or potentially life-threatening, according to the grading scale in [Table 10](#).

If a fever of  $\geq 39.0^{\circ}\text{C}/\geq 102.1^{\circ}\text{F}$  is recorded by a subject during the 7-day post-injection e-diary period, a telephone contact should occur to ascertain further details and determine whether a site visit is clinically indicated. Only an investigator or medically qualified person is able to confirm a trial subject's fever as  $>40.0^{\circ}\text{C}/>104.0^{\circ}\text{F}$  for recording in the trial database. If a trial subject experiences a confirmed fever  $>40.0^{\circ}\text{C}/>104.0^{\circ}\text{F}$ , the investigator must immediately notify the sponsor and, if it is determined to be related to the administration of IMP, further IMP injections will be discontinued in that trial subject.

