#### **10.3.1.6 Use of the terms “severe” and “serious”**

Severity (intensity or grade) and seriousness need to be assessed independently for each AE and be recorded in the CRF. For a definition of the terms “severe” and “serious” for AEs, see:

- Section [10.3.1.7](#) for AEs.
- Section [10.3.1.4](#) for SAEs (see Section [10.3.1.10](#) for SAE reporting instructions).

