3.1.1.3 Adverse events and serious adverse events

For all dosed trial subjects in cohorts 1-8, AEs will be collected from each dose up to 1 month after this dose and for subjects in cohort 9 - from the Visit 1 (after eligibility is confirmed) up to 1 month. However, for any visit more than 1 month after each IMP injection (cohorts 1-8) or Visit 1 (cohort 9), only IMP-related AEs, trial procedure-related AEs, adverse events of special interest (AESIs), SAEs, and AEs linked to confirmed COVID-19 cases will be recorded.

Solicited AEs (i.e., reactogenicity events) that are derived from trial subjects' e-diaries should not be reported as AEs unless the event meets criteria for an SAE or starts after Day 7 or starts on Days 1 to 7 and continues past Day 7.

In addition, all solicited Grade 4 reactogenicity events should be medically confirmed.

An AE/SAE is defined as treatment-emergent adverse event (TEAE) if the event onset date and time is after the first IMP dose (if the event was absent before the first administration of the IMP) or worsened after the first IMP dose (if the event was present before the first administration of the IMP).

In the event of an incomplete onset date, the event will be considered as treatment-emergent unless the partial onset date information or complete or partial end date confirms the onset date or the event end prior to the first dose of IMP.

Missing AE date will be addressed as described in [Section 5.3](#).

All AEs and SAEs will be coded/categorized according to terms in Medical Dictionary for Regulatory Activities (MedDRA®) version 26.0 or higher.

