6.1.1.1 Safety overview

The number of events, number and percentage of subjects reporting at least one of the below events from IMP administration will be summarized by treatment group post each dose and combined total of events for the periods from each dose up to 1 month after each dose based on Safety Set.

- Solicited local reactions and systemic events
- Any TEAE
- Related TEAE
- TEAE with Grade ≥ 3
- Related TEAE with Grade ≥ 3
- Any solicited AE that starts on Days 1 to 7 and continues longer than 7 d post-vaccination or starts after Day 7 or is an SAE
- Any SAE
- Related SAE
- SAE with Grade ≥ 3
- Related SAE with Grade ≥ 3
- TEAE leading to trial withdrawal
- TEAE leading to treatment withdrawal
- Any AESI
- All cause death

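### The SAP's two TEAE-withdrawal rows can miss withdrawals caused by short, non-serious solicited reactions

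*Protocol*

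**What the plan says.** Protocol 8.3 sets the recording rule: "Solicited events that are derived from the subject e-diaries should not be additionally reported as AEs unless the event meets criteria for an SAE". The sentence goes on to two timing exceptions: "or starts after Day 7 or starts on Days 1 to 7 and continues past Day 7". SAP 3.1.1.3 carries the same rule for reactogenicity events, which "should not be reported as AEs unless the event meets criteria for an SAE or starts after Day 7", or if they begin in the first week and last beyond it. Neither document adds an exception for a reaction that leads to stopping IMP or leaving the trial.

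SAP 3.1.1.3 makes AE status a precondition for TEAE status: "An AE/SAE is defined as treatment-emergent adverse event (TEAE) if the event onset date and time is after the first IMP dose". The SAP 6.1.1.1 overview then lists "TEAE leading to treatment withdrawal" and a matching row for withdrawal from the trial. The same table has a row for solicited AEs, limited to an event that starts in the first week and "continues longer than 7 d post-vaccination or starts after Day 7 or is an SAE".

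Protocol 8.2.3.2 attaches a dosing consequence to one solicited reaction, a confirmed fever above 40.0°C: "if it is determined to be related to the administration of IMP, further IMP injections will be discontinued in that trial subject". On grade against seriousness, Protocol 10.3.1.6 states: "Severity (intensity or grade) and seriousness need to be assessed independently for each AE".

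**The concern.** The recording rule is meant to avoid entering the same reaction twice, once from the e-diary and once as an AE. That is reasonable for counting reactions. It causes a difficulty when a later table uses the AE record to find out why someone stopped. The withdrawn-drug action in Protocol 10.3.1.7 is documented as a result of an AE, so a reaction with no AE record has nowhere to carry it.

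The error runs in one direction: the rows can be too low, never too high, for this reason. These are tolerability rows, and a zero or very small count in a multi-dose cohort could be read as showing that nobody stopped because of a vaccine reaction.

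**Working it through.** The plan states no figure on this point, so there is none to reproduce. The check is mainly a reading of the rules together, followed by a count of the subjects exposed to the gap.

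**Step 1. Which reactions that end dosing or participation reach the rows** (Protocol 8.3; SAP 3.1.1.3 and 6.1.1.1)

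| Solicited reaction | AE record expected? | In a TEAE-withdrawal row? |
|---|---|---|
| Meets SAE criteria, any duration | Yes | Yes |
| Starts after Day 7 | Yes | Yes |
| Starts on Days 1 to 7, continues past Day 7 | Yes | Yes |
| Starts and resolves by Day 7, not serious | No | No, unless the site records it anyway |

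Only the last line is a gap.

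**Step 2. Whether the fever in Protocol 8.2.3.2 can fall in that line.** In Protocol Table 10, Grade 4 fever is defined by temperature alone, whereas Grade 4 for the other systemic reactions involves an emergency room visit or hospitalization. Grade and seriousness are assessed separately (10.3.1.6). Under 10.3.1.4, life-threatening means actual risk of death at the time, not a hypothetical one. A related fever above 40.0°C that resolves within the week can therefore stop dosing without being an SAE. It can also be assessed as an SAE, and is then in the row.

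**Step 3. Whether another planned summary restores the link.** SAP 6.1.1.2 and 6.1.1.3 report reactions by severity, duration and onset, but not by consequence. SAP 6.5.2.1 reports discontinuations with primary reasons. The reasons in Protocol 7.1.1 and 7.2 contain no category for a solicited reaction. SAP 3.3.1 includes adverse event among the reasons for end of trial. If that category were used for a short reaction, disposition would show an AE-caused exit with no matching TEAE in the overview.

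**Step 4. Scope.** A later injection can be withheld only where more than one is planned (SAP 3.1.1; planned sizes in Protocol 9.2):

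- Part A Cohort 2 (about 20) + Part A Cohort 6 (about 20) + Part B Cohort 6 (about 375) = 415.
- Planned to be dosed: 120 (Part A) + 1,125 (Part B) + 180 (Part C Cohorts 7 and 8, 90 each) = 1,425.
- Share: 415 / 1,425 = 29%.

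The trial-withdrawal row could in principle be affected in any dosed cohort.

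**Step 5. Size, under assumed rates.** The documents give none.

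- Fever above 40.0°C: doses followed by another planned dose = 415 first doses + 395 second doses (Cohort 6 in Parts A and B, 20 + 375) = 810. At an assumed 0.01% to 0.1% per dose, the expected number is 810 × 0.0001 = 0.08 to 810 × 0.001 = 0.8. The chance of at least one is 1 − (1 − p)^810, about 8% to 56%. This takes every such fever as related, non-serious and resolved by Day 7, so at these rates it is an upper bound.
- Any short reaction that ends dosing: at an assumed 0.5% to 2% of subjects, 415 × 0.005 = 2.1 to 415 × 0.02 = 8.3, or about 2 to 8 subjects.

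**The case against.** The strongest reply is that little is lost. The overview's first row counts solicited reactions, the reactogenicity tables and listings show them by subject and severity, disposition shows who stopped and the primary reason, and SAP 5.2 promises individual listings of all relevant data. A determined reader could join them. This stands: what is missing is the attribution in a summary, not the events.

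The recording rule also says should, which the protocol's Notes for the Reader define as recommended rather than mandatory. A site may record a dose-stopping reaction as an AE without a deviation, and Protocol 10.3.1.7 asks that clinically significant findings be documented as AEs. This stands too, and makes the undercount expected rather than certain. It also means that sites may differ, which favours an explicit derivation.

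Three stronger readings are tempting, and the documents do not support them:

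- A reader might infer that reactions resolving by Day 7 are never recorded as AEs. The SAE exception is in the rule itself, and Protocol 10.3.1.4 is broad: important medical events usually count as serious.
- A reader might infer that the fever above 40.0°C is always absent from the row. Separate assessment of grade and seriousness does not make it non-serious. Its status depends on the investigator's assessment.
- A reader might infer that a primary safety result is biased. The primary safety endpoints in SAP 3.1.1 are local reactions, systemic events, AEs and SAEs. Withdrawal is a descriptive row with no hypothesis attached.

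Finally, Protocol 7.1.1 separates stopping IMP from leaving the trial, 8.2.3.2 stops only injections, and 7.2 expects withdrawals to be uncommon. The effect on the trial-withdrawal row is therefore likely to be slight.

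**Conclusion.** The point holds as a limited reporting gap. If sites follow the stated rule, a non-serious solicited reaction that starts and resolves by Day 7 and leads to stopping IMP or leaving the trial falls outside both TEAE-withdrawal rows. The rows can only be too low on this account. The treatment-withdrawal row is exposed in about 415 of the roughly 1,425 subjects planned to be dosed.

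The number actually missed is probably small. The ranges in Step 5 rest on assumed rates and should not be read as estimates from this trial. The conclusion also assumes that the rows are derived from the action recorded against an AE. How the CRF captures discontinuation reasons is not visible in the documents. This is a cheap improvement, not a threat to the safety conclusions.

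**What to change.** Make the change in the SAP and study report only. SAP 8.3 states that a protocol amendment was no longer possible and that the trial ended globally on 04 October 2023, so a new exception in Protocol 8.3 could not create records now.

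- In SAP 6.1.1.1, define the two withdrawal rows as the number and percentage of subjects whose discontinuation of IMP, or of the trial, was due to a TEAE or a solicited reaction. Derive them from the recorded discontinuation reason together with the AE and e-diary data.
- Show separately how many of these were due to a solicited reaction with no AE record.
- Where the recorded reason is non-specific, list the discontinued subjects with their e-diary reactions. Footnote the row to say that non-serious solicited reactions starting and resolving by Day 7 are not expected to have an AE record, and point to the disposition table.

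The cost is a little extra programming and some listing review, using data already collected. No change to the clinical stopping rule is implied.

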### **8.3.1 Time period and frequency for collection of AE, AESI, and SAE information**

All AEs, AESI, and SAEs (including a death) will be recorded at the time points listed in the SoA in Section 1.3.

For subjects who receive a non-trial SARS-CoV-2 vaccination, AEs/SAEs will be collected as specified above until the date when the subject was vaccinated with the non-trial SARS-CoV-2 vaccine. The AEs/SAEs expected to be captured after non-trial SARS-CoV-2 vaccination are within the frame of post-marketing safety data reporting.

Cohort 9 subjects will be offered a booster vaccination with the locally marketed Pfizer-BioNTech RNA-based COVID-19 vaccine after the EOT has been completed. If subjects choose to receive this vaccination, the recording and follow-up of any safety events will

follow post-marketing rules and such events will not be recorded within the trial documentation.

Investigators are not obligated to actively seek AEs or SAEs at any time after a trial subject has been discharged from the trial, however, if the investigator learns of any SAE (including a death), that they consider to be reasonably related to the IMP administration or trial participation, the investigator must promptly notify the sponsor.

### **8.3.2 Method of detecting AEs and SAEs**

The method of recording, evaluating, and assessing causality of AEs and SAEs and the procedures for completing and transmitting SAE reports are provided in Section 10.3.

Care will be taken not to introduce bias when detecting AEs and/or SAEs. Open-ended and non-leading verbal questioning of the trial subject is the preferred method to inquire about AE occurrences.

### **8.3.3 Follow-up of AEs and SAEs**

After the initial AE/SAE report, the investigator is required to proactively follow each trial subject at subsequent visits/contacts. All AEs/SAEs will be followed until resolution, stabilization, the event is otherwise explained, or the trial subject is lost to follow-up (as defined in Section 7.3). Further information on follow-up procedures is provided in Section 10.3.1.7.

The investigator is obligated to perform or arrange for the conduct of supplemental measurements and/or evaluations as medically indicated or as requested by the sponsor to elucidate the nature and/or causality of the AE or SAE as fully as possible. This may include additional laboratory tests or investigations, histopathological examinations, or consultation with other healthcare professionals.

New or updated information will be recorded in the originally completed CRF.

The investigator must submit any updated SAE data to the sponsor within 24 h of receipt of the information as indicated in Section 10.3.1.10.

All ongoing AEs/SAEs will be followed until resolution, considered by the investigator to be stable or chronic (resolved with sequelae), the trial subject is lost to follow-up or the trial subject withdraws consent. If no final status is reached by the time the trial subject is discharged from the trial, the investigator must confirm the unavailability of a final status.

### **8.3.4 Regulatory reporting requirements for SAEs**

Prompt notification of an SAE/AESI via the provided SAE/AESI form by the investigator to the sponsor within 24 h of the site's awareness is essential so that legal obligations and ethical responsibilities for the safety of trial subjects, and the safety of a trial treatment under clinical investigation and regulatory reporting obligations are met.

The sponsor has a legal responsibility to notify both the local regulatory authority and other regulatory agencies involved in the conduct of trials with the same IMP about the safety of a trial treatment under clinical investigation. The sponsor will comply with country-specific regulatory requirements relating to safety reporting to the regulatory authorities, Institutional Review Boards (IRBs)/Independent Ethics Committees (IECs), and

investigators. The execution of expedited reporting to the different entities may be delegated as detailed in the trial Safety Management Plan.

All serious adverse reactions, the nature, severity or outcome of which is not consistent with the reference safety information are “unexpected serious adverse reactions”. The expectedness assessment for all related SAEs is based on the reference safety information included in Section 7.8.2 of the current [BNT162 IB](#).

Safety reports will be prepared for suspected unexpected serious adverse reactions (SUSARs) according to local regulatory requirements and sponsor policy and forwarded to investigators as necessary.

For the IMP, it is the sponsor’s or delegate’s responsibility to perform SUSAR reporting to the applicable regulatory authorities, IECs/IRBs, within the timelines stipulated in the respective country regulations. Reporting to the investigators will follow country-specific regulatory requirements and applicable guidelines.

An investigator who receives an investigator safety report describing an SAE or other specific safety information (e.g., summary or listing of SAEs) from the sponsor should review it and then file it together with the IB. If required by local requirements, the investigator will notify the relevant IECs/IRBs.

### **8.3.5 Pregnancy testing and handling of pregnancies**

For WOCBP, pregnancy tests will be performed using commercial kits at the times given in the SoA (see Section [1.3](#)).

Pregnancy information (information on trials subjects who become pregnant or information for female partners of male trial subjects who become pregnant) will be collected for pregnancies that occurred after the date of the first injection of IMP until the subject terminates or completes the trial.

Pregnancy information will only be collected after obtaining written informed consent from the pregnant female subject (or if a male subject’s partner becomes pregnant, written informed consent from both).

As described in Section [7.1.1](#), subject pregnancy will trigger permanent discontinuation of IMP administration.

If a pregnancy is reported, the investigator should inform the sponsor within 24 h of learning of the pregnancy and should follow the procedures outlined in Section [10.4](#).

Abnormal pregnancy outcomes (e.g., spontaneous abortion, fetal death, stillbirth, congenital anomalies, ectopic pregnancy) are considered SAEs.

### **8.3.6 Death events**

Any death that occurs within the observation period will be reported as an SAE.

In case of a fatal event, the event term should not be “death” but the underlying event which led to death (death = outcome). If there is more than one AE in a fatal case, only for the AE leading to death the outcome “fatal” should be selected. If the cause of death is

unknown and cannot be ascertained at the time of reporting, “unexplained death” should be documented as event term.

### **8.3.7 Disease-related events/outcomes not qualifying as AEs or SAEs**

Not applicable.

### **8.3.8 Adverse events of special interest**

The following will be reported as AESIs:

- Myocarditis (all Levels of Certainty including “Possible cases” (1 to 3) as per Brighton Collaboration Case Definition) 1 to 3 (Possible Case), Myocarditis\_Version\_1.0\_15 July 2021\_FINAL\_for Posting)
- Pericarditis (all Levels of Certainty including “Possible cases” (1 to 3) as per Brighton Collaboration Case Definition) 1 to 3 (Possible case), Pericarditis\_Version\_1.0\_15 July 2021\_FINAL\_for Posting)
- Anaphylaxis
- Thromboembolic events (e.g., deep vein thrombosis, stroke, myocardial infarction)
- Immune thrombocytopenia
- Immune based neurologic events (e.g., optic neuropathy, Guillain-Barré syndrome)

If an AESI is reported, the investigator should inform the sponsor as outlined in Section 10.3.1.10. For the treatment of myocarditis and pericarditis, see Section 8.5.

